#### *Interview questions:*

- 1) After hearing what moral injury is (*remind them if necessary*), how important do you think this problem is in this health facility or in the province?
  - a. probe: In your opinion, how common do you think this experience of moral injury might be among HCW in this area?
  - b. probe: Have you ever experienced moral injury/ moral trauma? If so, please can you describe your experience?
  - c. probe: How does it impact HCW’s mental health (e.g., depression, anxiety, apathy, etc.)?
  - d. probe: How does it affect the way they deliver care? (e.g., do they seem to have less empathy for patients? Do they have greater frustration with or depersonalization of patients?)
- 2) Do you know of any HCW who have become suicidal or had thoughts of suicide? If so, can you tell me about their experiences?

3) What are the biggest issues with working in the health field and in this health system in particular that could be causing high levels of moral injury? How have these issues impacted you?

- a. probes: Lack of medication, lack of materials, lack of human resources, work atmosphere, management issues, level of support from supervisors, others?
- b. probe: Are there any other minor issues related to working in the health field that could be causing moral injury? If so, can you describe how these impact you?

4) We understand that the health system is under capacitated, but we still want to support HCW. In your opinion, what could be done to reduce either the experience of or the impact of moral injury on HCW?

- a. Some changes have to be done at the health system level- like making sure there are enough drugs or hiring more people to help deliver care. What suggestions would you have to improve the health care system?
  - i. Do you think this would be feasible to implement?
- b. Some services could be provided to individual HCW who are struggling- like offering counseling or support services to them specifically.
  - i. How can we help HCW who feel lots of anxiety or depression?
  - ii. How can we help HCW who feel like the health system is failing patients?
  - iii. How can we help HCW who have thoughts of suicide or become suicidal?
    - 1. Do you think any of these would be acceptable to HCW? Would they be feasible to implement?

5) In our recent survey, we found low levels of burnout among HCW at several HF in the area. Burnout is characterized by a high degree of emotional exhaustion (e.g., fatigue, lack of motivation) and depersonalization (i.e., not caring for each patient as an individual, or cynicism) and a low sense of personal accomplishment at work. In many areas around the world, HCW have high levels of burnout, but here only 1% of participants showed moderate levels of burnout. Why do you think HCW in Zambézia show low levels of burnout?

- a. probe: Do you think that HCW in this area have ways of avoiding burnout/ staying resilient within their work? If yes, what are some of those the ways?

## Appendix 9: Routinely collected clinical data of all PLHIV to be extracted from EPTS (Objective 2)

1. Age
2. Sex
3. Date of HIV diagnosis
4. Education level (highest completed)
5. Marital status
6. Number of children alive
7. HIV status disclosed to family (yes/no)
8. ART initiation date
9. ART pick up dates (all during study period)
10. Scheduled ART pick up dates (all during study period)
11. Clinical appointment dates (all during study period)
12. Scheduled clinical appointment dates (all during study period)
13. Viral Load test results and dates (all during study period)
14. Pregnancy status at time of study.
15. Differentiated model of care (all documented during study period)
16. Type of drug dispensation (all documented during study period)
17. Blood pressure (all results during study period)
18. Weight (all results during study period)
19. Height
20. TB treatment
21. WHO staging
22. patient ID
23. CD4 results and dates (all during study period)

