People living with HIV (survey): The study team will recruit participants to complete the baseline and endline surveys at the time the individuals are leaving an appointment for HIV care at one of four eligible health care facilities. Recruitment will be done using convenience sampling when the individual exits the health facility after receiving care. If the individual is interested in participating in the study, a study assistant will bring them into a private room to discuss their eligibility and study procedures (complete surveys at study baseline or endline, i.e., 6 months after the study begins, and to the use of a subset of data from their medical records regarding ART medication pick-up history within the previous 6 months). If eligible and they agree to participate, their informed consent will be obtained by the study assistant at the health facility. Participants can withdraw at any time without impact on the clinical care they are receiving.

People living with HIV who are followed as part of routine care (estimated n=16,000): The study team will not formally recruit and consent these individuals to participate in the study, as only a chart review will be performed. For the inclusion of these individuals' data, we will seek a waiver of informed consent, to be developed and included in the submission to the ethics committees/Institutional Review Board (IRB), to access their retention data and viral load results over the course of the study.

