#### **Objective 2:**

With Objective 2 most of our outcomes are continuous measurements, and analyses will be similar to those described above: linear mixed effects models that take advantage of the factorial nature of outcome, with clusters defined as study sites, and unadjusted and adjusted for a small number of PLHIV-level covariates (age, sex, educational level, marital status, language, duration on ART, and history of ART medication pick-ups within the previous 6 months). For binary outcomes (e.g., undetectable viral load), we will fit generalized linear mixed effects models with a logit link function.

Every patient is given 30, 60, 90, or 180 days to pick up their ART medication, as indicated in the medical charts. If a patient picks up medication after the indicated/scheduled date, they will be considered "non-adherent" for each day after their specific pick-up date; this will be assessed over the course of the 6-month follow-up and will be treated as a continuous variable (a proportion between 0 and 1 for each participant). Participants who are lost to follow-up from the health facility during the 6-month follow-up period will be considered "non-adherent" for the days that they are lost. For persons who die or are known to have transferred care outside of the catchment area, the proportion of time on medication will be computed using only time prior to death or transfer of care. For our primary retention outcome (proportion of time on medication), normality assumptions are unlikely to hold, perhaps even after data transformation. Hence, we will fit a cumulative probability model (CPM) with fixed effects for the clinics. The CPM is well-suited for this setting because it does not require symmetry/normality in the outcome (which is bounded between 0 and 1 and likely not normal); in the absence of covariates, it reduces to the Wilcoxon rank sum test. The CPM has been shown to perform well in settings investigating medication adherence. Specifically, the distribution of the proportion of time on medication will be modeled as

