$\text{logit}(P(Y \leq y)) = \beta_0(y) + \beta_1 \text{Intervention} + \beta_s \text{site} + \beta_x X$ , where  $\beta_1$  is the effect of the intervention on the log-odds ratio scale. Our primary objective is to test the null hypothesis,  $H_0: \beta_1 = 0$ . We will provide estimates of  $\beta_1$ , 95% Wald confidence intervals, and two-sided p-values. As with our other analyses, we will take advantage of the factorial nature of the model by grouping interventions as receiving resilience intervention (yes vs. no) and receiving anti-stigma intervention (yes vs. no). An interaction between the two interventions will also be assessed to see, for example, if the interventions are synergistic. The primary model will be adjusted for study site to acknowledge similarities between patients at the same site, and it will also be adjusted for a small number of patient-level baseline covariates, that are usually predictive of adherence to medications (e.g., age, sex, and education). In the model with the interaction between two interventions, study site will not be included so that the interaction effects are identifiable. In additional crude secondary analyses, we will investigate how changes in HCW measures correlate with patient outcomes by including average HCW metrics in models, replacing study site with this continuous variable. These latter analyses will be very much exploratory, as with only four study sites, we will have limited information to estimate these associations.

We will also compute three secondary measures of patient retention:

- (1) Monthly medication pick-up. Specifically, measured from the first day of ART initiation, any ART medication pick-up between days 16 and 45 will count as medication pick-up during month 1, any medication pick-up between days 46 and 75 will count as medication pick-up during month 2, and so forth, up until 6 months (i.e., medication pick-up between day 346 and 375); if the patient was enrolled on a three month pick up we will calculate on time pickups using the mark 15 days before and 15 days after the scheduled visit.

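### The Objective 2 covariate list is not tied to a population, and Appendix 9 as written gives the chart cohort neither pre-study pick-up history nor language

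*Combined protocol and SAP*

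**What the plan says.** Section 10 (Data Analysis, Objective 2) opens with a general statement: "With Objective 2 most of our outcomes are continuous measurements, and analyses will be similar to those described above". It then describes mixed models adjusted for age, sex, educational level, marital status, "language, duration on ART, and history of ART medication pick-ups within the previous 6 months". The same paragraph continues: "For binary outcomes (e.g., undetectable viral load), we will fit generalized linear mixed effects models with a logit link function". Viral load is a chart outcome, and no separate covariate list is given for it.

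The primary adherence outcome, proportion of time on medication, has its own model, a cumulative probability model (CPM). It is adjusted for study site and for baseline covariates described as "usually predictive of adherence to medications (e.g., age, sex, and education" and so on.

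Appendix 9 lists the fields extracted for all patients. Item 9 reads "ART pick up dates (all during study period"; scheduled pick-ups (item 10) and viral loads (item 13) carry the same limit. Language is not listed. Section 7.e words the waiver of consent as a request "to access their retention data and viral load results over the course of the study", and the Section 15 timeline collects routine data in Months 1-12.

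For survey participants, Appendix 2 records maternal language and Appendix 10 extracts actual and scheduled pick-ups for the preceding six months.

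**The concern.** If the Objective 2 list applies to chart-cohort models such as viral suppression, two of its covariates are not in the extract that feeds them. A programmer working from Appendix 9 would have to drop pick-up history or build it from pick-ups within the study period. The second course conditions on post-randomisation data and, for adherence, on the outcome itself.

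Whichever population the list was meant for, following Appendix 9 leaves the primary adherence analysis with no pre-study value of its own outcome. Each arm is one facility, so any difference in adherence that existed before the trainings is confounded with intervention. Prior adherence is the natural covariate for that problem. Section 10 already adjusts for the baseline outcome in Objective 1 and calls the Objective 2 analyses similar.

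**Working it through.** **Matching covariates to data sources**

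| Objective 2 covariate | Chart cohort (Appendix 9) | Survey sample (Appendices 2 and 10) |
|---|---|---|
| Age | yes | yes |
| Sex | yes | yes |
| Education | yes | yes |
| Marital status | yes | yes |
| Language | no | yes |
| Duration on ART | yes, from ART start date | yes, from ART start date |
| Pick-ups, previous 6 months | no, study period only | yes |
| Total | 5 of 7 | 7 of 7 |

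Of the covariates named for the primary CPM, 3 of 3 are in Appendix 9.

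**Reproducing the plan's own figure**

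Inputs from Section 7.c: m = 4,000 patients per site, ICC 0.05, two-sided alpha 0.05, 80% power. Section 10 compares two sites with two, so k = 2 per group. With outcome SD 1 and a normal approximation:

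SE = sqrt[(2/k)(ICC + (1 − ICC)/m)] = sqrt(0.05 + 0.95/4000) = 0.224 SD

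Detectable difference = (1.960 + 0.842) × 0.224 = 0.628 SD

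The plan states 0.64 SD, at which this formula gives 81.5% power. For ICC 0.025 and 0.10 it gives 0.445 and 0.887 SD against the stated 0.45 and 0.91. The plan's figures reproduce, and none depends on a baseline covariate.

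**Adding pre-study adherence as a covariate**

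The documents give no covariate strength, so these are assumed shares of within-site (Rw) and between-site (Rb) variance explained:

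Detectable difference = 2.80 × sqrt[ICC(1 − Rb) + (1 − ICC)(1 − Rw)/m]

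- Rb = 0, with Rw rising from 0 to 0.5: 0.6279 falls to 0.6272 SD, no material gain.
- Rb = 0.3: about 0.53 SD.
- Rb = 0.5: about 0.44 SD.

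With 4,000 patients per site, nearly all the variance of the contrast is between sites, so only the between-site part of the covariate matters.

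**A site-level before-after contrast**

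SE = sqrt[2·ICC·(1 − CAC) + 2(1 − ICC)(1 − r)/m]

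Here CAC is the correlation of a site's level between periods and r the patient-level correlation. Both are assumptions. With r = 0.5 the second term is 0.95/4000 = 0.00024.

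| Assumed CAC | SE before-after (SD) | Against 0.224 follow-up only |
|---|---|---|
| 0.4 | 0.245 | about 10% larger |
| 0.5 | 0.224 | equal |
| 0.6 | 0.201 | about 11% smaller |
| 0.8 | 0.142 | about 37% smaller |
| 0.9 | 0.101 | about 55% smaller |

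The sign of the effect on precision turns on a quantity that the documents do not give.

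**The case against.** The strongest reply is that the list was written for the survey models. It matches the survey data 7 of 7, and Section 8.a says that the six-month pick-up history is taken for analysing the survey. On that reading each appendix fits its own analysis. This is plausible, but Section 10 does not say it, and the same paragraph covers undetectable viral load. Nor is the survey reading free of difficulty: endline respondents are interviewed at 6-7 months and may be different people, so their preceding six months fall in the intervention period.

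A reader might infer that the primary analysis cannot be run as planned. The documents do not support that. The CPM names only age, sex and education, as examples, and nothing calls pick-up history its key covariate. A reader might also infer that the history cannot be obtained. That too goes too far. Section 8.a describes the routine extract as open-ended and mentions pick-up records without a date limit, and the same OpenMRS system supplies six prior months for survey participants. What stands is that Appendix 9 sets an explicit window, and neither the waiver wording nor the timeline provides a look-back.

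Two further points stand. Section 7.b admits to the chart cohort only patients currently in care, whereas follow-up counts those who become lost as non-adherent, so the two periods are not fully comparable. And Sections 8.a and 12 already present this as a pilot limited by having four sites.

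**Conclusion.** There is an unresolved mismatch between the Objective 2 text and Appendix 9, and a missed opportunity in the primary adherence analysis. Two of seven listed covariates cannot be supplied for the chart cohort from the extract as specified. The primary model can be fitted as described, but it has no pre-study measure of adherence with which to address existing differences between four single-site arms.

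The case for adding that measure is handling baseline imbalance between sites, not a promised gain in power. It would be tempting to claim that a before-after analysis cuts the standard error by 37% or 55%. Those figures require an assumed site autocorrelation of 0.8 or 0.9; at 0.5 there is no gain and at 0.4 a loss. They also describe a linear contrast in SD units that the plan does not propose, whereas the CPM works on the log-odds scale. This should be corrected, but it does not invalidate the design.

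**What to change.** 1. In Section 10, state which covariates apply to the chart-cohort models and which to the survey models. Confine language to the survey models unless the electronic record is confirmed to hold it.
2. Extend Appendix 9 items 9 and 10, and item 13 for viral load, to the six months before the first session. The control site has no sessions, so set its index date explicitly.
3. Amend the waiver wording in Section 7.e and the data-collection window in Section 15 to match.
4. Compute the pre-study proportion of time on medication and enter it as a baseline covariate in the chart-cohort models, including the CPM. State the rule for patients who started ART less than six months earlier.
5. If a site-level before-after contrast is reported, label it a sensitivity analysis, with the autocorrelation caveat and the effect of the in-care entry criterion stated.

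The cost is a wider date filter on an existing query and a small protocol and waiver amendment. Recent ART starters will have incomplete history, and four sites remain few whatever is adjusted for.

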- (2) Monthly medication pick-up using a “re-setting” of the ART medication pick-up timeframe for each subsequent month. Specifically, calculating next scheduled ART medication pick-up from the date of last (most recent) ART pick-up (*data to be obtained from “master card” documentation*), any ART medication pick-up between days 16 and 45 from next scheduled date will count as medication pick-up for that specific month. With each date of last (most recent) ART pick-up, the window for next scheduled medication pick-up will adjust accordingly;
- (3a) For patients on monthly medication pick up. Retention at 6 months based on Mozambique Ministry of Health (MoH) guidelines. Specifically, at days 180 and 365 if the patient has had a documented ART pick-up within 59 days of their last scheduled pick-up date (*data to be obtained from pharmacy FILA form*), then they will be considered retained at that time point. If the patient has not had a documented ART pick-up in  $\geq 60$  days from their last scheduled pick-up date, they will be considered not retained (i.e., lost to follow-up);
- (3b) For patients on a differentiated care model. Retention at 6 months will look at the most recent ART medication pick-up that occurred during the first 180 days and the date of the next scheduled pick-up falling within the 180 days or beyond; if that day falls before day 121 after initiating ART, the patient would not be considered retained at 6 months.

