## Appendix 10: Clinical data to be extracted from EPTS for only the PLHIV participating in the survey (Objective 2)

1. Patient ID
2. Date of enrollment in HIV services
3. ART initiation date
4. ART pick up dates (all in previous 6 months)
5. Scheduled ART pick up dates (all in previous 6 months)
6. Differentiated model of care (all in previous 6 months)
7. Viral Load test results and dates (all in previous 6 months)
8. Type of drug dispensation (all documented in previous 6 months)

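### The routine-cohort extract holds no pick-up or scheduled dates from before the study period, so the primary adherence rule has no starting date for patients already overdue when the 6-month window opens

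*Combined protocol and SAP*

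**What the plan says.** Section 10 (Data Analysis, Objective 2) defines the primary measure, proportion of time on medication. The trigger is "If a patient picks up medication after the indicated/scheduled date", and the patient is then non-adherent "for each day after their specific pick-up date; this will be assessed over the course of the 6-month follow-up". Days on which a patient is lost to follow-up also count as non-adherent. For death or transfer out, "the proportion of time on medication will be computed using only time prior to death or transfer of care".

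Appendix 9 lists the data to be extracted for the routine cohort of about 16,000 patients. Item 9 is "ART pick up dates (all during study period") and item 10 is "Scheduled ART pick up dates (all during study period"). Appendix 10, for survey participants only, asks for "Scheduled ART pick up dates (all in previous 6 months") and the matching actual pick-ups.

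Section 7b admits patients who are active in care and not in default, with no number of days attached. The only lapse threshold is in secondary retention measure (3a): "If the patient has not had a documented ART pick-up in" 60 days or more from the last scheduled date, the patient is not retained. The opening day of the 6-month window is not stated. Section 15 has routine data collected over Months 1-12.

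**The concern.** The scoring rule needs the date on which each overdue spell began. For a patient already overdue on day 0, that date lies before the study period and is not on the Appendix 9 list. Three things then cannot be derived from the listed fields: the overdue days between day 0 and the first pick-up in the window, the date on which a loss to follow-up began, and whether the patient was in default at entry.

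This bears on the primary patient outcome. The patients affected are those already late, who are plausibly at higher risk of being lost. How many there are depends on each site's backlog, and Section 6 allocates one site to each arm. A backlog difference between sites would therefore enter the comparison in a form that the extract could not reveal.

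**Working it through.** **The plan's own figure.** Section 7c gives 0.64 SD as detectable at about 80% power for this outcome, with m = 4,000 per facility, ICC 0.05 and two sites against two. (1.960 + 0.842) × √[2(1 + 3,999 × 0.05)/(2 × 4,000)] = 2.802 × √0.05024 = 0.628 SD, and power at 0.64 SD is 81.5%. The figure reproduces. It does not depend on how dates are extracted, so this point does not affect it.

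**Scoring single patients (180-day window).** Score = (180 − late days in window)/180.

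- Patient A: due 20 days before day 0, returns on day 25, on time afterwards. With the pre-window date: (180 − 25)/180 = 155/180 = 0.861.
- Patient A on the literal extract, unflagged days counted as on medication: 180/180 = 1.00.
- Patient A on the literal extract, days before the first in-window pick-up dropped from the denominator: 155/155 = 1.00.
- Patient A on the literal extract, those days treated as missing: no score without a further rule.
- Other patients overdue on day 0 who return on day 10, 30 or 58: 170/180 = 0.944, 150/180 = 0.833 and 122/180 = 0.678 with the pre-window date. Each scores 1.00 on either of the first two literal readings.
- Control case, due on day 5 and collected on day 15: 170/180 = 0.944 either way. The gap affects only patients overdue when the window opens.

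**Effect on the cohort mean.** Overstatement = share overdue at day 0 × mean uncounted days / 180. Both inputs are assumptions. For example, 2% × 7/180 = 0.0008, 10% × 15/180 = 0.0083 and 20% × 58/180 = 0.064.

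**Narrowing the range.** Refill histories were simulated in steady state with these inputs:

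- From the documents: 87% in care at 12 months (Section 4), applied as a constant loss rate, so loss per refill = 1 − 0.87^(supply/365); supplies of 30 or 90 days (Section 10).
- Assumed: 20-40% of refills late; exponential lateness with mean 7-20 days; default meaning 60 days or more overdue, taken from measure (3a); window opening at study start.

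| Patients who never return | Non-adherent days uncounted | Mean adherence overstated |
|---|---|---|
| Captured by the loss-to-follow-up rule | about 1-9% | about 0.05 to 2 points |
| Not captured | about 15-34% | about 2 to 4 points |

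A hand check explains the gap between the rows. The daily loss rate is −ln(0.87)/365 = 0.00038. Over the 60 days in which a lost patient is not yet in default, that is about 60 × 0.00038 = 0.023, so about 2% of the cohort are eligible on day 0 but never return. Each has 180/180 of the window uncounted, which is about 2 points.

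**Sensitivity to the default threshold** (30% late, mean 15 days, never-returners not captured): the uncounted share falls to 12-19% at 30 days and about 7-11% at 15 days. If any overdue day counts as default, nobody overdue at day 0 is eligible and the scoring gap closes. The pre-window date would still be needed to apply that exclusion.

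**The case against.** The case on the other side has real force.

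- **No stated wrong score.** A reader might infer that the plan scores these overdue days as on medication. Nothing says so. The rule in Section 10 refers to the date in the medical chart and, with that date in hand, gives Patient A 0.86. The defect is an undefined case together with an extract list that cannot resolve it. This stands.
- **Never-returners.** A reader might infer that an overdue patient who never returns scores 1.00. The loss-to-follow-up rule covers such patients, so the larger figures apply only if it fails to capture them. This stands, although dating the start of the loss also needs the missing date.
- **The list is open.** Section 8a describes the routine data as not confined to its list, and Section 10 names pick-ups over the previous 6 months as a covariate, so earlier dates are contemplated. This is partly right. Earlier dates are permitted but not required, and Section 8a refers to Appendix 9 for its pick-up records.
- **Day 0 is undefined.** Extraction runs for 12 months. If the 6-month window opens after Month 1, some or all of the needed dates fall inside the extract. This stands as an uncertainty about size. Sections 7e and 8a place the endline survey about 6 months after study start, which suggests an early window but does not settle it.
- **Confounding by site.** The same extract applies at all four sites, and the limits of a four-site design are acknowledged in Sections 8a and 12. A reader might infer a demonstrated bias in the training contrast; the documents give no backlog by site, so none is shown.
- **Late entrants.** A reader might also infer a wrong denominator for patients who start ART during the window. For a start on day 120 with 30 days' supply followed by loss, a fixed window that credits pre-ART days gives 150/180 = 0.83, time since initiation gives 30/60 = 0.50, and a personal 6-month window gives 30/180 = 0.17. The plan states none of these, so this is unspecified detail.

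**Conclusion.** The gap is real. On the listed fields, lateness, the start of loss and default status cannot be derived for a patient whose scheduled date precedes the window, and no rule says how the affected days are scored. The same two fields have a 6-month look-back for survey participants but none for the cohort that carries the primary adherence outcome.

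The effect is probably small: about 0.05 to 2 percentage points of mean adherence if the loss-to-follow-up rule works as intended, and about 2 to 4 points if it does not. Both ranges rest on assumed lateness, on a 60-day threshold borrowed from a secondary measure, and on a window that opens at study start. A stricter default threshold reduces them. They describe the mean; the primary model works on the log-odds scale, and no effect on its estimate has been derived.

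This is a cheap improvement to make before extraction. Neither its size nor the wording of the plan supports treating it as an error that invalidates the primary analysis.

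**What to change.** 1. In Appendix 9, items 9 and 10, add for every patient the last ART pick-up before the window opens and the scheduled date set at that pick-up. Alternatively, use the 6-month look-back of Appendix 10, which would also supply the previous-6-months pick-up covariate wherever the Objective 2 models are fitted to the routine cohort.
2. In Section 10, Objective 2, define day 0 of the 6-month window. State that an eligible patient overdue on day 0 is non-adherent from day 0 until pick-up, and that eligible patients with no in-window record stay in the analysis under the loss-to-follow-up rule.
3. In Section 7b, state the number of overdue days that constitutes default for eligibility, so that it can be checked from the extracted dates.
4. Optionally, state how the denominator starts for patients who begin ART or transfer in during the window, alongside the existing rule for death and transfer out.

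The cost is at least one more pre-window record per patient from OpenMRS (several with the 6-month look-back), a few sentences of text, and slightly lower reported adherence. No new data collection is needed. It is easier to do before the de-identified dataset is sent for analysis than afterwards.
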